9.8. ECG

Assessment of Standard 12-lead ECG are obtained at visits per [Table 3](#). A central ECG Standard 12-lead ECG will record heart rate (HR), PR interval, RR interval, QT interval, Fridericia's corrected QT interval (QTcF), and QRS duration. The overall ECG assessment will be centrally reported as "Normal" or "Abnormal". If a post-baseline QTcF value >500 msec or change from baseline >60 msec is found, the investigator should repeat the ECG assessment twice. In this case, the confirmed QTcF, defined as the average of all 3 ECG values at the visit, will be used for summary.

Baseline for ECG assessment is the parent study baseline.

Observed results of each ECG parameter and change from baseline will be summarized by visit using descriptive statistics.

In addition, for QTcF, average baseline confirmed QTcF (the average of the parent study screening and baseline QTcF), and the change from average baseline will be summarized visit using descriptive statistics.

QTcF values will be classified as having QTc prolongation according to the following conditions.

QTc Prolongation
Confirmed QTcF >450 msec
Confirmed QTcF >480 msec
Confirmed QTcF >500 msec
Increase from baseline QTcF \geq 60 msec
Increase from average baseline confirmed QTcF \geq 60 msec
Increase from baseline QTcF \geq 30 msec
Increase from average baseline confirmed QTcF \geq 30 msec

The number and percentage of patients with QTc prolongation will be summarized by visit.

A shift table comparing the overall ECG assessment from baseline to each visit will be presented.

In addition, the markedly abnormal post-baseline ECG results will also be summarized for patients with at least one markedly abnormal value during the treatment period. The summary will be completed by the age groups (6 - < 8 years, 8 - < 12 years, and 12 - < 16 years) at the time of the individual assessment.

Criteria for markedly abnormal values used in the study are presented in [Table 8](#).

This document is confidential.

Table 8: Criteria for Abnormal ECG Parameters by Age

ECG parameter (unit)	Age (years old)	Abnormally Low	Abnormally High
HR (bpm)	6 to <8	< 65	> 115
	8 to <12	< 55	> 110
	12 to <16	< 50	> 105
	≥16	< 50	> 100
PR interval (msec)	6 to <8	--	> 160
	8 to <12	--	> 175
	12 to <16	--	> 180
	≥16	--	> 200
QRS interval (msec)	6 to <8	--	> 100
	8 to <12	--	> 105
	12 to <16	--	> 110
	≥16	--	> 120

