6.1. General Methods

Statistical methodology and analyses are in accordance with the principles outlined by the ICH E9 guidelines. All statistical analyses will be conducted using SAS statistical software version 9.4 or above.

Tables, listings and figures (TLFs) will be produced in accordance with the principles outlined by the ICH E3 guidelines.

Data summaries will use descriptive statistics (number of patients [n], mean, standard deviation [SD], standard error [SE], median, minimum, and maximum) for continuous variables, and frequency and percentage of patients for categorical and ordinal variables, unless otherwise specified. For continuous variables, if $n < 5$ then only median, min and max will be presented.

Unless otherwise specified, all statistical tests will be two-tailed using a 0.05 level of significance. All confidence intervals (CIs) will be two sided 95% CIs.

Only visits mapped to scheduled visits will be included in by-visit summaries. All visit assessment data will be included in shift tables and will appear in the patient listings.

In general, endpoints assessed in Parts I and III will be summarized for Parts I and III combined and endpoints assessed in Part II will be summarized separately for Part II.

For assessments conducted at each visit, analyses for Parts I and III combined will include Week 28 assessment, but Week 30 assessment will not be included. Summary for Part II will include Week 28 (the randomized withdrawal baseline) and Week 30.

For analyses performed by time period, the date of Week 28 and Week 30 will be considered as the first and last day of Part II, respectively. Summary for Parts I and III combined will not include period between Week 28 assessment and Week 30 assessment, which will be covered under Part II summary.

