	Day after Part II first dose (or Date of randomization, if first dose date is missing) - Week 30 visit date (or Day 224 if subject terminated before Week 30 visit)	Day 210	Week 30
	Day 225 - 262	Day 238	Week 34/Part III
	Day 263 - 332	Day 287	Week 41
	Day 333 - 382	Day 378	Week 54
	≥Day 383	Day 385	Week 55
Vital sign, Weight, Height	Day 2 - 21	Day 14	Week 2
	Day 22 - 35	Day 28	Week 4
	Day 36 - 49	Day 42	Week 6
	Day 50 - 80	Day 56	Week 8
	Day 81 - 150	Day 105	Week 15
	Day 151 – Date of first dose of double-blind IMP (or Date of randomization, if first dose date is missing) if patient is randomized; Day 151 – Day 203 if	Day 196	Week 28/Beginning of Part II

This document is confidential.

Statistical Analysis Plan for Interventional Studies

Sponsor: Teva Branded Pharmaceutical Products R&D, Inc./Nuvelution TS Pharma, INC.
 Protocol No.: TV50717-CNS-30047

Assessment	Study Day Window	Scheduled day	Scheduled Visit/Week
	patient is not randomized		
	Day after Part II first dose (or Date of randomization, if first dose date is missing) - Week 30 visit date (or Day 217 if subject terminated before Week 30 visit)	Day 210	Week 30
	Day 218 - Day 231	Day 224	Week 32
	Day 232 - 262	Day 238	Week 34/Part III
	Day 263 - 332	Day 287	Week 41
	Day 333 - 382	Day 378	Week 54
	≥Day 383	Day 385	Week 55
ECG	Day 2 - 42	Day 28	Week 4
	Day 43 - 126	Day 56	Week 8
	Day 127 - 287	Day 196	Week 28
	≥ Day 288	Day 378	Week 54
Chemistry/ Hematology/ Urinalysis	Day 2 - 126	Day 56	Week 8
	Day 127 - 287	Day 196	Week 28
	≥ Day 288	Day 378	Week 54

After mapping the data to the analysis visits of unscheduled and early termination visits, the following rules will apply unless other handling is specified for a particular analysis.

- If there is a scheduled visit in the analysis window, the scheduled visit will be selected.
- If there is no scheduled visit, but an early termination visit, the early termination visit will be selected.
- If there are no scheduled or early termination visits, the record closest to the planned assessment day will be selected for analysis.
- If there are no scheduled or early termination visits, and 2 records are equidistant from the scheduled day, then the later record will be selected.
- If a patient has no scheduled record or early termination/unscheduled visits in an analysis window, the patient will be considered missing at that visit.

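### QTcF outliers are counted only by visit, so early-termination or unscheduled ECGs that share a window with a scheduled ECG never enter the counts; the ECG age bands also stop short of Table 8

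*SAP*

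**What the plan says.** Section 9.8 sets seven QTcF criteria: three absolute thresholds (above 450, 480 and 500 msec) and increases of at least 30 or 60 msec from two versions of baseline. They are reported in one way: "The number and percentage of patients with QTc prolongation will be summarized by visit". The same section plans a second ECG outlier display, "summarized for patients with at least one markedly abnormal value during the treatment period". Its limits are given as follows: "Criteria for markedly abnormal values used in the study are presented in" Table 8. That table has rows for heart rate, PR and QRS, and no row for QTcF. The ECG shift table covers only the overall Normal/Abnormal reading.

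Section 6.4 decides which ECG represents a visit. Early-termination and unscheduled records are mapped to windows, and then "If there is a scheduled visit in the analysis window, the scheduled visit will be selected". An early-termination record is taken only when the window holds no scheduled one, and other records only when it holds neither. The preamble allows exceptions: "the following rules will apply unless other handling is specified for a particular analysis". Section 9.8 specifies none for QTcF. Section 6.1 adds "Only visits mapped to scheduled visits will be included in by-visit summaries" and, for the remaining records, "All visit assessment data will be included in shift tables and will appear in the patient listings".

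On age, the text of Section 9.8 splits the markedly abnormal summary into three bands: 6 to under 8, then "8 - < 12 years, and 12 - < 16 years) at the time of the individual assessment". Table 8 has a fourth band, 16 and over, with its own limits for all three parameters.

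**The concern.** The primary objective is long-term safety and tolerability, and QTcF is the one ECG parameter given several outlier thresholds of its own. A reader of the report will want to know how many patients ever crossed each one. By-visit rows do not answer that, because the same patient may or may not recur from row to row. The selection rule adds to the problem: an ECG taken when a patient leaves, or because an investigator asked for one, gives way to a routine ECG that may be weeks or months older. The plan already uses an any-time count for vital signs (Section 9.7, Parts I and III combined) and for heart rate, PR and QRS. QTcF alone lacks one.

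The age bands raise a smaller matter. Read literally, an abnormal heart rate, PR or QRS at age 16 or over has a limit in Table 8 but no band in the summary that applies it.

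**Working it through.** The SAP states no figure on this point, so there is none to reproduce. The check uses the ECG windows in Section 6.4 and the schedule in Table 3 (ECGs at Day 1 and Weeks 4, 8, 28 and 54, plus early-termination and discretionary unscheduled ECGs).

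**Days on which an early-termination ECG is displaced.** It loses if it falls after the scheduled ECG but inside the same window: days = window end − scheduled day.

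| Visit | Window | Nominal day | Days displaced |
|---|---|---|---|
| Week 4 | 2-42 | 28 | 42 − 28 = 14 |
| Week 8 | 43-126 | 56 | 126 − 56 = 70 |
| Week 28 | 127-287 | 196 | 287 − 196 = 91 |
| Week 54 | 288 onward | 378 | 0 up to Day 378 |

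The sum is 14 + 70 + 91 = 175. Day 2 to Day 378 is 378 − 2 + 1 = 377 days, and 175/377 = 46%. If every scheduled ECG is 3 days early the sum is 17 + 73 + 94 = 184 (49%). If every one is 3 days late it is 11 + 67 + 88 = 166 (44%).

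**Unscheduled ECGs.** The four windows leave no gap. A patient with all four scheduled ECGs therefore has every unscheduled ECG left out of the QTcF table, whether taken before or after the scheduled one.

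**One patient traced through.** Suppose a Week 28 ECG on Day 196 is unremarkable, and an early-termination ECG on Day 250 shows QTcF above 500 msec.
1. Day 250 lies in 127-287, so it maps to Week 28.
2. That window already holds a scheduled ECG, which is selected.
3. There is no Week 54 ECG.
4. The patient meets no QTcF criterion in any row.

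No ECG is scheduled between Weeks 28 and 54. For a patient with a Day 196 ECG, every ECG on Days 197-287 meets the same fate. That span covers randomized withdrawal, the blinded re-titration and the start of open-label maintenance.

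**By-visit against any-time counts.** The SAP gives no QTcF event rate, so this is an assumption shown as a range. With a per-visit proportion p, the same at four visits, the any-time proportion lies between p (always the same patients) and 1 − (1 − p)^4 (independent visits).

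| p | Independent visits |
|---|---|
| 0.5% | 2.0% |
| 1% | 3.9% |
| 2% | 7.8% |
| 3% | 11.5% |

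A by-visit table cannot show where in that range the trial lies, even before any displaced ECG is considered.

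**Age bands side by side.** The Section 9.8 text gives 6 to <8, 8 to <12 and 12 to <16. Table 8 gives the same three and also ≥16. Section 7.2 has parent-baseline ages up to 16 and ages in this study up to 18. Bands are assigned by age at each assessment, so assessments at 16 or over are to be expected.

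**The case against.** Much can be said for the plan, and part of it stands.

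- **Nothing is deleted.** A reader might infer that displaced ECGs disappear from the report. They do not: Section 6.1 keeps them in the listings, and their overall reading goes into the shift table. A QTcF finding reported as an adverse event would also enter the tables in Section 9.4, and Section 4.1 has the IDMC monitoring safety during the study. This stands. But a listing gives no count or percentage, and the shift table carries no QTcF value.
- **The windows look wide but are not faulty.** Each cut-point is the midpoint between scheduled ECGs: (28 + 56)/2 = 42, (56 + 196)/2 = 126, (196 + 378)/2 = 287. The width comes from a sparse schedule. This stands, and the windows need no change.
- **The 46% does not measure missed events.** It counts calendar days. On the other 54% an early-termination ECG is used, because no scheduled ECG has yet been taken in that window. This stands.
- **A reader might infer that these ECGs are where QTc findings leading to discontinuation appear.** The SAP says nothing to support that, and the point does not need it.
- **The age-band list may be only a wording slip.** Section 9.8 names Table 8 as the source of the criteria, and older patients remain in the by-visit descriptive statistics and the shift table. That is fair. It is an inconsistency to correct, not evidence that older patients' ECG data go unreported.
- **A pooled worst-value row could mix treatments.** An ECG in Part II may follow placebo, and the SAP keeps Part II apart from Parts I and III. This stands and shapes the fix.

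**Conclusion.** The point holds in a limited form. Followed as written, the plan gives no count of patients who ever met a QTcF criterion. It leaves out of its only QTcF outlier table any early-termination ECG taken after the scheduled one in its window, and any unscheduled ECG sharing a window with a scheduled one. For early-termination ECGs the exposed span is 175 of 377 days at nominal visit timing (166 to 184 if visits shift by 3 days either way). How many outliers this would miss is unknown, since the SAP gives neither a QTcF event rate nor the number of such ECGs. The documents do not support the stronger readings that data are lost from the report or that the windows are misdrawn.

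The age-band mismatch is a separate, minor inconsistency. Its reach cannot be sized, because the SAP gives no age distribution. The any-time count should be added because it changes a reported safety result; the age band is a text correction.

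**What to change.** In Section 9.8, for each QTcF criterion, add a count and percentage of patients meeting it at any post-baseline ECG, over all scheduled, unscheduled and early-termination ECGs. State that the selection rules of Section 6.4 do not apply to this summary, which their own preamble permits. Define the value to use: the three-ECG average where repeats were triggered, and the single value otherwise. The second half is needed because the SAP defines confirmed QTcF only for the triggered case, yet applies it to the 450 and 480 msec thresholds as well.

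Present the count for Parts I and III combined. Show any ECGs taken during Part II separately by actual treatment received, as Section 5.4 requires for Part II safety data. Keep the by-visit table and the windows as they are.

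Separately, add the 16-and-over band to the age list in the Section 9.8 text so that it matches Table 8.

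The cost is a few extra rows and one age band. No new data are needed, and no error rate or design feature changes. Reported outlier counts may rise.

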9.9. Physical Examination

Physical examinations are performed at visits per [Table 3](#). Physical examinations will be listed.

9.10. Neurological Examinations

Neurological examinations will be performed at visits per [Table 3](#). Neurological examinations will be listed.

9.11. Children’s Depression Inventory, Second Edition (CDI-2)

The CDI-2 (parent and self-report versions) is administered per [Table 3](#). As the CDI-2 is designed for children 7 to 17 years of age, children 6 years of age at baseline will not complete the Self-report version; the caregiver/adult will complete the Parent version.

The CDI-2 self-report is a 28-item self-report questionnaire assessing depressive symptoms in children 7 to 17 years of age with basic reading and comprehension skills. In the CDI-2, children are asked to choose 1 of 3 statements that most closely aligns with their feelings in the previous 2 weeks. The CDI-2 Self-report version contains 6 subscales (emotional problem, negative mood/physical symptoms, negative self-esteem, functional problems, ineffectiveness, and interpersonal problems). The raw score is the sum

This document is confidential.

of all subscales scores, ranging from 0 to 56, with higher score indicating more severe depressive symptoms. The raw score is normalized to T-score (range: 40-90) based on patient's age and gender.

The CDI-2 parent is a 17-item questionnaire administered to parents to assess depression-related behaviors observed in their children. In the CDI-2 Parent, parents are asked to rate their child's behaviors in the past 2 weeks on a 4-point Likert scale from "not at all" to "much or most of the time". The CDI-2 parent version contains 2 subscales (emotional problems and functional problem). The raw score is the sum of the 2 subscales, ranging from 0 to 51, with higher score indicating more depression-related behaviors observed in their children. The raw score is normalized to T-score (range: 40-90) based on patient's age and gender.

The CDI-2 parent version and self-report versions subscale scores, raw scores, and self-report version T scores will be summarized at each visit.

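### The CDI-2 self-report raw score is defined as the sum of all six listed subscales, which fits the stated 0 to 56 range only if no item sits in more than one of them

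*SAP*

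**What the plan says.** SAP Section 9.11 describes two forms of the CDI-2.

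- **Self-report.** "The CDI-2 self-report is a 28-item self-report questionnaire assessing depressive symptoms", in which "children are asked to choose 1 of 3 statements that most closely aligns with their feelings". On structure: "The CDI-2 Self-report version contains 6 subscales (emotional problem, negative mood/physical symptoms, negative self-esteem, functional problems, ineffectiveness, and interpersonal problems". Section 9.11 then builds this form's total by adding up these parts, as the sum "of all subscales scores, ranging from 0 to 56", and converts it to a T-score (range 40 to 90) by age and gender.
- **Parent.** "The CDI-2 parent is a 17-item questionnaire", rated "on a 4-point Likert scale". On structure: "The CDI-2 parent version contains 2 subscales (emotional problems and functional problem". Here the total adds those two subscales and runs from 0 to 51.

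Raw and subscale scores for both forms, and T-scores for the self-report, are summarised at each visit. Section 4.1 names observed values and changes in the CDI-2 as safety endpoints for Parts I and III and again for Part II. Section 10.1 repeats them for the interim analysis.

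**The concern.** The summation rule and the range stand in the same sentence, and they agree only if the six subscales share no items. The SAP does not say that they share none, and two features of Section 9.11 suggest that they do:

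- The parent form has only the emotional and functional subscales, and these two are its whole total. The same two names appear among the six self-report subscales.
- The self-report list gives emotional problem and then two narrower domains, followed by functional problems and then two narrower domains. That is the order one would use for two broad scales, each followed by its components.

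On that structure, a programmer who follows the written rule adds the broad scales and their components together. The result would be a doubled raw score for a named safety endpoint, in a study whose primary objective (Section 3.1) is long-term safety and tolerability, and a wrong input to the T-score. No item-sum rule appears in Section 9.11 to override the subscale sum.

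**Working it through.** **Inputs (all SAP Section 9.11).** Self-report: 28 items, 3 statements per item, 6 subscales, total equal to the sum of all subscales, range 0 to 56. Parent: 17 items, 4-point scale, 2 subscales, range 0 to 51. Item codes are not given, so scoring from zero (0 to 2 and 0 to 3) is an assumption implied by the stated ranges.

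**Step 1: reproduce the stated ranges.** With each item counted once, maximum = number of items × highest item score.
- Self-report: 28 × 2 = 56, as stated.
- Parent: 17 × 3 = 51, as stated.
- Coding the self-report items 1 to 3 would give 28 to 84, which does not match.

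The 0 to 56 range is therefore right for 28 items scored 0 to 2, each counted once.

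**Step 2: the rule if the six subscales do not overlap.** Each item enters one subscale, so the sum of six is the item sum, 0 to 56. Rule and range agree, and the inflation factor is 1.

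**Step 3: the rule if the two broad scales contain the other four (assumption).** Let E and F be the emotional and functional scores, with E = a + b and F = c + d, where a to d are the four narrower scores. Then

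sum of six = E + F + a + b + c + d = 2(E + F).

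The maximum is 2 × 56 = 112. This does not depend on how the 28 items divide between E and F. For example, 8 and 20 items give 2 × 2 × 8 + 2 × 2 × 20 = 32 + 80 = 112, and 14 and 14 give 56 + 56 = 112. The inflation factor is 2.

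**Step 4: partial overlap.** If every item falls in at least one and at most two of the six subscales, the factor for a given patient lies between 1 and 2.

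**Step 5: what the tables would show under Step 3.**

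| True value | Value under the literal rule |
|---|---|
| Raw score 20 | 40 |
| Worsening of 5 points | 10 points |
| Raw score 28 | 56, still within the stated range |
| Raw score 29 | 58, outside the stated range |

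A range check at 56 would flag only true scores above 28. At 28 or below, the doubled value passes unnoticed and goes into the T-score conversion.

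**The case against.** The strongest reply is that Section 9.11 gives the six subscales as one flat list and never says that two of them contain the other four. The parent form is a different questionnaire (17 items on 4 points against 28 items with 3 statements), so two shared names do not show how the self-report items are divided. If the subscales are distinct, the text is correct as written. Even if they are nested, the item count and the 0 to 56 range both point to one count per item, and an attentive programmer would sum items. The CDI-2 is also summarised descriptively, and no test or decision rule uses the raw score.

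Much of this stands. The nesting is an assumption and the doubling is conditional on it. What does not stand is the claim that the range protects the derivation: Step 5 shows that it catches only true scores above 28. The range is also a check on the result, whereas the subscale sum is the only instruction given.

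A reader might infer three stronger points that the SAP does not support:

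- **That the planned score is in fact doubled and cannot have its stated range.** This needs the nesting as a fact, and the SAP does not state it.
- **That T-scores would be unobtainable, or too high by a known amount.** The conversion table is not shown. All that follows is that the input would be wrong.
- **That leaving parent T-scores out of the summary gives six-year-olds, who have the parent form only, no depression result.** Parent raw and subscale scores are summarised. Limiting T-scores to the self-report is an explicit choice, and Section 9.11 gives the instrument's design ages as 7 to 17, so norms at age 6 are not established.

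**Conclusion.** The point holds as a conditional fault in the derivation wording. The 0 to 56 range is correct, but the summation rule beside it is safe only if the six subscales are disjoint, and the SAP's own description makes overlap the more natural reading. Under full nesting the literal rule gives 0 to 112 and doubles every self-report raw score and change. With no overlap there is no error, so the inflation lies between 1 and 2 times. This rests on items scored 0 to 2 (implied by the range) and, for the upper end, on the broad scales containing the other four (supported by the parent form and the list order, but not stated). The documents do not show that a doubled score is what the sponsor intends to compute. The wording should be corrected because it defines a named safety endpoint and the error could pass a range check. Parent raw and subscale scores are not affected.

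**What to change.** In Section 9.11, replace the subscale sum with an item sum: the self-report raw score is the sum of the 28 item scores, each scored 0 to 2, range 0 to 56, and this value is used for the T-score. Add a sentence saying which subscales, if any, are made up of others, confirmed against the instrument's scoring instructions, and that such component subscales are reported separately and not added again. The SAP need not assert that the total equals emotional plus functional problems, because its present text does not establish this for the self-report.

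The item-sum rule is correct whether or not the subscales overlap. The cost is a change of wording and one derivation, with no new data: Section 9.12 already plans to summarise a single self-report item, which implies that item responses are held.
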